6.3 Eligibility Criteria

The population to be enrolled in this study includes patients who present to the hospital with a submassive pulmonary embolism with symptom onset within 14 days. Patients 18 years of age and older will be evaluated for this study and must meet all inclusion criteria and will have none of the exclusion criteria.

6.3.1 General Inclusion Criteria

All answers must be YES to the inclusion criteria below:

1. Willing and able to provide informed consent;
2. 18 years of age and less than 75 years of age;
3. PE symptom duration \leq 14 days;
4. Filling defect on at least one main or lobar pulmonary artery as determined on contrast enhanced chest CT Scan (CTA);
5. RV/LV diameter ratio ≥ 0.9 by contrast enhanced chest CT scan (CTA) as determined by the investigative site;
6. Willing and able to comply with all study procedures and follow-up.

6.3.2 General Exclusion Criteria

All answers must be NO to the exclusion criteria below:

1. Cerebrovascular Accident (CVA) or transient ischemic attack (TIA) within one (1) year;
2. Head trauma, or other active intracranial or intraspinal disease within one (1) year;
3. Recent (within one month) or active bleeding from a major organ;
4. Intracranial condition(s) that may increase the risk of bleeding (e.g., neoplasms, arteriovenous malformations, or aneurysms);
5. Patients with bleeding diathesis;
6. Hematocrit $< 30\%$;
7. Platelets $< 100,000/\mu\text{L}$;
8. INR > 1.5 ;
9. aPTT > 50 seconds in the absence of anticoagulants;
10. Major surgery within fourteen (14) days;

11. Serum creatinine > 2.0 mg/dL;
12. Clinician deems high-risk for catastrophic bleeding;
13. History of heparin-induced thrombocytopenia (HIT);
14. Pregnancy;
15. Systolic blood pressure < 90 mmHg for greater than 15 minutes;
16. Vasopressor support;
17. Cardiac arrest (including pulseless electrical activity and asystole) requiring active cardiopulmonary resuscitation (CPR);
18. Evidence of irreversible neurological compromise;
19. Life expectancy < one (1) year;
20. Use of thrombolytics or glycoprotein IIb/IIIa antagonists within 3 days prior to inclusion in the study;
21. Use of non-vitamin K oral anti-coagulants (NOACs), such as rivaroxaban, apixaban, dabigatran, edoxaban within 48 hours prior to inclusion in the study;
22. Use of enoxaparin sodium injection (Lovenox[®]) within 12 hours of procedure start time;
23. Profound bradycardia requiring a temporary pacemaker and/or inotropic support;
24. Previous enrollment in this study;
25. Morbidly obese (BMI >45 kg/m²) patient who by the judgement of the investigator is high risk for bleeding;
26. Absolute contraindication to anticoagulation;
27. Uncontrolled hypertension;
28. Currently participating in another study;
29. In the opinion of the investigator, the subject is not a suitable candidate for the study.

6.4 Study Duration

6.4.1 Enrollment

It is estimated that up to five (5) sites will enroll a total of ten (10) subjects over nine (9) months.

6.4.2 Follow-up

The follow-up for each subject will be completed at one (1) month post-discharge.

6.4.3 Complete Study Period

It is estimated that this study will require eleven (11) months to complete enrollment and follow-up.

6.4.4 Subject Participation

Each subject will participate in this study for approximately 30 days from consent through 30-day follow-up.

7.0 METHODOLOGY

7.1 Pre-Procedure Testing Within 48 Hours Pre-Procedure

7.1.1 Laboratory Tests

1. **CMP, CBC, Cardiac Biomarkers Troponin I and BNP** – These tests will be drawn within 48 hours pre-procedure.
2. **aPTT** – Drawn within 48 hours pre-procedure. Unfractionated heparin will be infused to prolong the aPTT (suggested range is 60-80 seconds) prior to the administration of r-tPA. The institution is to follow the standard of care for the administration of heparin through the completion of the r-tPA infusion and the monitoring of aPTT in addition to the aPTTs measured at certain time points required by this protocol.
3. **International Normalized Ratio (INR)** – INR will be drawn within 48 hours pre-procedure for patients who are on Coumadin and must be ≤ 1.5 to be eligible for enrollment. Patients who are on Coumadin and have an INR ≤ 1.5 who are in the study the coumadin will be discontinued during the heparin infusion and the r-tPA infusion and can be restarted prior to discharge.
4. **Fibrinogen** – Fibrinogen levels are required to be checked within 48 hours prior to the procedure. *The assay method must be recorded (e.g. Clauss, PT-derived fibrinogen assay, immunological, gravimetric, other)*

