7.1.6 Data Collection

The following data will be collected and documented in the CRF in addition to the required pre-procedure testing.

1. **Informed Consent** – required for all study subjects prior to any testing that is not the standard of care.

2. **Demographics and Medical History** – Recorded once Informed Consent has been obtained.
3. **Eligibility Criteria** – all inclusion criteria must be met, and all exclusion criteria must not be met to enroll in this study.
4. **Medications** – All medications will be recorded within 48 hours pre-procedure, at baseline.
5. **Modified Miller Index (MMI)** – Modified Miller Index (MMI) will be calculated by the core lab at baseline. The contrast enhanced chest CTA will be sent to the core lab and the MMI will be calculated by the core lab for each contrast enhanced CTA of the chest done in this study.²¹

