10.0 POST-PROCEDURE PATIENT MANAGEMENT AND TESTS

The study subject will be admitted to the intensive care unit (ICU) where nursing staff are experienced in the care of patients treated for pulmonary embolisms.

10.1 r-TPA Infusion – Intensive Care Unit

1. **r-tPA Infusion:** Maintain the r-tPA Infusion through the infusion line on the side of the handle of the BEC in the ICU for approximately eight (8) hours from start of the infusion in the IR suite/Cath lab. The infusion should run at the rate prescribed in this protocol until the infusion is complete.
 - a. **Unilateral PE:** Infusion rate is to be maintained at 95cc/hour through the BEC, for a total of 1.27mg/hour infusing into the patient over approximately eight (8) hours. (95cc/hr= 1.27mg/hour x 1 infusion x approximately 8 hours = 10mg total). Infuse the r-tPA mixture until the infusion is complete.
 - b. **Bilateral PE:** Infusion rate is to be maintained at 0.65mg/hour through each catheter, for a total of 1.3mg/hour infusing into the patient (0.65mg/hour through each BEC). This is a rate of 65cc/hour per infusion for a total of 130cc/hour total infusing through two catheters into the patient. Infuse the r-tPA mixture until the infusion is complete
2. **Laboratory Tests:** Four (4) hours (\pm 1 hour) after initiation of heparin infusion started in the IR suite/Cath lab measure:
 - a. CBC
 - b. aPTT
3. **Hemodynamic Readings:** Record the following pressures in the ICU beginning with the 1st reading two (2) hours (\pm 30 minutes) after the initiation of the r-tPA infusion and then every thirty (30) minutes (\pm 15 minutes) thereafter through the central lumen of the BEC. If a waveform, or both waveforms (if bilateral) appear damped, verify each BEC pressure transducer is set up properly when study subject arrives in ICU. If the waveform continues to be damped, document the date and time when the waveform becomes phasic and print the waveform from the monitor. Mark on the waveform where the systolic PA, diastolic PA, and mean PA pressures are read and retain with the source documentation for this study. Please note that when the waveform becomes phasic, it must be documented even if it outside of the “every 30 minutes” scheduled readings. This is so the length of time from the 1st pulse spray (in the Cath/IR lab) to when the

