10.3 Tests Required at End of Infusion(s) and 24 Hours After r-tPA Infusion

10.3.1 Laboratory Tests and Other Tests

1. **BMP, CBC, Cardiac Biomarkers Troponin I and BNP** – These tests will be drawn 24 hours (± 8 hours) after completion of the r-tPA infusion.
2. **aPTT** – To be drawn once heparin gtt is stopped according to standard of care and ONLY IF it is standard of care to check aPTT after heparin gtt is discontinued.

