21.0 APPENDICES

APPENDIX 21.1 REQUIRED STUDY PROCEDURES

Test	Pre-Procedure	Procedure	Post-Procedure	End of Infusion	24 Hrs Post-r-tPA Completion	48 Hrs Post-r-tPA Completion	72 Hrs Post- r-tPA Initiated	Before Discharge	30-day Follow-up
Visit Window	≤ 48 Hrs of procedure			+8 Hrs	± 8 Hrs	± 6 Hrs	-4 / +12 Hrs	-8 Hrs	± 7 Days
Informed Consent	X								
Demographics and Medical History	X								
Physical Examination	X			X	X			X	X
12 Lead ECG	X							X	
CBC, INR ¹	X		X ²		X				
aPTT	X ²		X	X					
Fibrinogen ³	X			X					
CMP	X								
BMP					X				
Cardiac Biomarkers: Troponin I, BNP	X				X				
Lower Extremity Venous DUS	X								
Contrast Enhanced CTA of the Chest	X						X		
RV/LV Diameter Ratio with each CTA	X						X		
Echocardiogram	X				X				
RV/LV Diameter Ratio with each Echocardiogram	X				X				
Eligibility Criteria	X	X							
Anticoagulation ³ (Heparin, Lovenox)	X	X	X	X	X	X			
IR / Cath Lab: Invasive Hemodynamic Data / ACT ⁴		X		X					
IR / Cath Lab: r-tPA Pulse Sprays Administration		X							
Bashir™ Endovascular Catheter(s) and r-tPA Use ⁵		X	X	X					
ICU: PAS / PAD / Mean PA q 30 Min via BEC			X	X					
ICU: Mixed venous SvO ₂ q2 Hours via BEC			X	X					
r-tPA Infusion		X	X						
Medications	X	X	X	X	X	X	X	X	X
AEs / SAEs		X	X	X	X	X	X	X	X
Contrast Enhanced CTs to Core Lab	X					X			
Echocardiograms to Core Lab	X				X				

¹INR is only required at baseline for patients on Coumadin (warfarin) and must be ≤ 1.5 prior to enrollment. If patient is eligible for the study, Coumadin will be discontinued temporarily for study purposes.

[figure not shown]
²Pre-procedure suggested aPTT 60-80s. Suggested aPTT during r-tPA administration is 40-60s. Check aPTT and CBC 4 hr (± 1 hr) after heparin is restarted in the IR suite/Cath lab (suggested range 60-80s).

[figure not shown]
³Unfractionated Heparin will be infused IV pre-procedure or Lovenox. Stop Heparin prior to start of procedure. Restart Heparin post procedure with r-tPA infusion. Fibrinogen to be drawn at time of BEC removal in IR suite/Cath lab. Heparin infusion will continue until the completion of the r-tPA infusion. Lovenox 1mg/kg Sub-Q will be started 45 minutes (± 15 minutes) from the completion of the r-tPA infusion and given q12hrs (± 30 min).

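### Exclusion 8 (INR above 1.5) applies to every candidate, but the plan requires an INR only from candidates on Coumadin

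*Combined protocol and SAP*

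**What the plan says.** **The criterion.** Exclusion 8, an INR above 1.5, appears without any condition in the synopsis (Section 1.0) and in Section 6.3.2. Section 6.3.2 opens its list with "All answers must be NO to the exclusion criteria below". Section 7.1.6 item 3 repeats the rule as a condition of entry: "all inclusion criteria must be met, and all exclusion criteria must not be met to enroll in this study".

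**The test.** Section 7.1.1 item 3 states that "INR will be drawn within 48 hours pre-procedure for patients who are on Coumadin", and the same sentence sets a value of at most "1.5 to be eligible for enrollment". Footnote 1 of Appendix 21.1 is more explicit: INR is needed only at baseline, and only in patients taking Coumadin.

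**The other screening tests.** Section 7.1.1 item 1 requires "CMP, CBC, Cardiac Biomarkers Troponin I and BNP" with no restriction on who is tested. Items 2 and 4 do the same for aPTT and fibrinogen.

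**The concern.** The criterion covers all candidates, while the test that would apply it covers only some of them. A site that follows the protocol to the letter must record that a candidate not on Coumadin does not have an INR above 1.5, although no section tells it to measure the INR.

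The treatment under study is a thrombolytic, and the primary safety endpoint (Section 6.2.1) is ISTH major bleeding within 72 hours of starting r-tPA. Exclusion 8 is one of the coagulation criteria that define the population in which bleeding is counted. If a NO can mean either a measured value of 1.5 or below or no measurement at all, that part of eligibility cannot be verified from required data. With up to five sites, the basis for the answer may also differ from site to site.

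**Working it through.** No formula applies and the plan gives no figure to reproduce. The check compares each numeric laboratory exclusion in Section 6.3.2 with the test that Section 7.1.1 requires.

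| Exclusion | Measure | Required test (Section 7.1.1) | Required in every candidate? |
|---|---|---|---|
| 6 | Hematocrit | CBC, item 1 | Yes |
| 7 | Platelets | CBC, item 1 | Yes |
| 8 | INR | INR, item 3 | No, Coumadin users only |
| 9 | aPTT | aPTT, item 2 | Yes |
| 11 | Creatinine | CMP, item 1 | Yes |

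Four of five have a test required in everyone; 5 − 4 = 1 does not, and that one is INR.

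**Is the criterion conditional?** Exclusion 9 shows how the plan writes a conditional criterion: it limits itself to patients not on anticoagulants. Exclusion 8 has no such words.

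**Is an INR required from everyone somewhere else?** The schedule in Appendix 21.1 has a combined row for CBC and INR with three marks: pre-procedure, post-procedure and 24 hours.

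- Pre-procedure: footnote 1 limits the INR part to Coumadin users.
- Post-procedure: footnote 2 says "Check aPTT and CBC 4 hr". Section 10.1 item 2 lists only CBC and aPTT as the tests that sites, four hours "after initiation of heparin infusion started in the IR suite/Cath lab measure".
- 24 hours: Section 10.3.1 asks for "BMP, CBC, Cardiac Biomarkers Troponin I and BNP", again without INR.

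So INR belongs to 1 of the 3 marks (baseline), and 3 − 1 = 2 are CBC only. The row does not supply the missing test.

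**Do other exclusions do the same job?** Exclusions 5 (bleeding diathesis), 12 (clinician-judged bleeding risk), 21 (recent NOAC use) and 29 (investigator opinion) may remove some of the same candidates. None of them sets an INR limit. Platelet count, aPTT and fibrinogen are measured in everyone, but none of them is an INR value.

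**How many subjects?** The documents do not give the proportion on Coumadin. Taking that proportion as unknown between 0 and 1, between 0 and 10 of the 10 subjects could be enrolled with no required INR behind the answer to item 8.

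**The case against.** The strongest reply is that an exclusion without a mandated test is not in itself a contradiction. Exclusion 14 (pregnancy) has no test in Section 7.1.1 or Appendix 21.1 either. On this reading, exclusion 8 applies to whatever INR the site has, and Section 7.1.1 adds a compulsory draw for the group most likely to have a raised value. Section 7.1.1 item 3 and footnote 1 agree with each other, which suggests that the restriction was deliberate. Sites may well have a routine INR, and the case report form, provided separately, may ask for one.

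Part of this stands. The restriction may be intended, and the content of the case report form cannot be judged from these documents. Different practice between sites is therefore a possibility and not a finding. It is also fair that a required test is not the same as a verified criterion: exclusion 9 does not apply to a candidate already on anticoagulants, even though an aPTT is drawn.

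The mismatch remains. INR is not merely left without a test, as pregnancy is; the plan states a testing rule that is narrower than the criterion it serves. Where the plan relies on standard of care, as for aPTT monitoring, it says so, and for INR it does not. If the restriction is intended, exclusion 8 is the text that is wrong, and an edit is needed either way.

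The column positions in the schedule could be doubted, since the chest CTA row is marked under a different time from the text. For the CBC and INR row, however, the marks agree with Sections 10.1 and 10.3.1, and the conclusion does not depend on them.

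**Conclusion.** The concern holds. Exclusion 8 applies to all candidates, the required INR applies only to those on Coumadin, and nothing else in the plan closes the gap. One of five numeric laboratory exclusions has no test required in every candidate, so a candidate not on Coumadin can be enrolled for r-tPA without the result that exclusion 8 depends on.

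The consequence is limited to the verification of eligibility, and so to the definition of the population behind the bleeding endpoint. The documents support no estimate of how often a candidate with an INR above 1.5 would be enrolled, and none is made. The sample size of ten and the descriptive analysis are unaffected. The conclusion rests on the text alone; the only assumption is the unknown Coumadin share behind the range of 0 to 10 subjects. The point should be corrected before enrollment.

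**What to change.** Reconcile the synopsis, Section 6.3.2, Section 7.1.1 item 3 and footnote 1 of Appendix 21.1, leaving the 1.5 limit unchanged. There are two ways to do it, and the sponsor must say which is intended.

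1. **Match the test to the exclusion as written.** Replace the first sentence of Section 7.1.1 item 3 with: *An INR is obtained from every candidate in the 48 hours before the procedure; enrollment requires a value of 1.5 or below.* Replace the first sentence of footnote 1 with: *INR is required at baseline only, in every candidate; enrollment requires a value of 1.5 or below.* Keep the sentences on Coumadin that follow in both places. The word *only* must stay in the footnote, so that the two later marks in that row still mean CBC alone.
2. **Match the exclusion to the test.** If exclusion 8 is meant only for patients on Coumadin, say so in the synopsis and in Section 6.3.2. Other candidates then have no INR screen, and the protocol should state this openly.

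**Cost.** Either route needs two text edits. The first adds one assay per candidate. It might use blood already drawn, but Section 7.1.1 does not say that samples are shared, so at worst it means one more tube. Where an INR is not standard of care, Section 7.1.6 item 1 requires consent before it is drawn. A few more screen failures are possible.

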7.1.2 Imaging

1. **Contrast Enhanced CTA of Chest** – A contrast enhanced CTA of chest will be performed within 48 hours pre-procedure. The contrast enhanced chest CTA is used to determine the pre-procedure Modified Miller Index Score within 48 hours prior to the procedure. *CT will be sent to the core lab for analysis.*
2. **Lower Extremity Venous DUS** – A duplex ultrasound is required pre-procedure to verify patency of the common femoral vein (CFV) for femoral access. The right CFV or the left CFV may be used for access, whichever is patent. If both of the CFVs are not patent, an internal jugular (IJ) vein may be used for access. IJ access may also be used if that is the operator's preference.
3. **Echocardiogram** – The echocardiogram will be done to determine the pre-procedure RV/LV end-diastolic diameter ratio. A core lab protocol will be followed for data acquisition. *The echocardiogram will be sent to the core lab for analyses.*

7.1.3 Assessments

1. **Physical Examination** – The physician will perform a physical exam within 48 hours prior to the procedure to ensure the subject meets eligibility criteria.
2. **RV/LV Diameter Ratio** – The RV/LV ratio will be measured within 48 hours pre-procedure by contrast enhanced chest CTA to ensure the subject meets the eligibility criteria of an axial RV/LV ratio ≥ 0.9 . RV/LV ratio is required to be assessed by contrast enhanced chest CTA to determine eligibility. The site determines eligibility, and an independent core lab protocol will be followed for data acquisition. *Both the contrast enhanced chest CTA and echocardiogram will be sent to the core lab for analysis.*
3. **12-Lead Electrocardiogram (ECG)** – A 12-lead ECG will be performed prior to the procedure.

7.1.4 Anticoagulation

Unfractionated heparin is required to be used for anticoagulation and is to be started pre-procedure by intravenous administration to prolong the aPTT (suggested range is 60-80 seconds) unless the patient has received Lovenox.

The institution is to follow the standard of care for the administration of heparin and the monitoring of aPTT in addition to the aPTTs measured at certain time points required by this protocol. Stop the heparin administration at the completion of the r-tPA infusion. The final aPTT should be measured according to standard of care.

7.1.5 Patients Receiving Lovenox for Treatment of Pulmonary Embolism

Lovenox: Use of Lovenox is permitted pre-procedure for the treatment of PE if it is the standard of care. If Lovenox is administered to a potential study subject, then catheter directed thrombolysis procedure is to start no sooner than 12 hours from the last Lovenox dose.

During the CDT procedure in the IR suite/Cath lab ACTs will be checked and heparin bolus given to achieve ACT ≥ 200 seconds.

After completion of the CDT procedure, a heparin drip will be started prior to leaving the IR suite/Cath lab to maintain therapeutic dose through completion of the r-tPA infusion.

7.1.6 Data Collection

The following data will be collected and documented in the CRF in addition to the required pre-procedure testing.

1. **Informed Consent** – required for all study subjects prior to any testing that is not the standard of care.

2. **Demographics and Medical History** – Recorded once Informed Consent has been obtained.
3. **Eligibility Criteria** – all inclusion criteria must be met, and all exclusion criteria must not be met to enroll in this study.
4. **Medications** – All medications will be recorded within 48 hours pre-procedure, at baseline.
5. **Modified Miller Index (MMI)** – Modified Miller Index (MMI) will be calculated by the core lab at baseline. The contrast enhanced chest CTA will be sent to the core lab and the MMI will be calculated by the core lab for each contrast enhanced CTA of the chest done in this study.²¹

8.0 IR SUITE/CATH LAB STUDY PROCEDURES

Should the patients meet all eligibility criteria for inclusion into the study, continue with the following procedures that take place in the IR suite/Cath lab.

8.1 Required Accessories and Supplies

8.1.1 Accessories to be provided by the IR suite/Cath lab

1. Introducer Sheath(s) - 7F or greater and of appropriate length. The sheath selected must reach the target site and allow for retraction of the BEC to expose the infusion basket. A 70 cm length sheath Flexor® Raabe Guiding Sheath (Cook Medical, Inc.) or equivalent for femoral access is recommended for most patients. A shorter sheath may be utilized for IJ access.
2. Ultrasound for ultrasound guided access is required for both IJ and CFV access.
3. Micropuncture kit for IJ and CFV venous access is required for both IJ and CFV access.
4. Guidewire - .018in x 300cm in length minimum (Hi-torque Steelcore Peripheral Guide Wire Abbott Vascular or equivalent).
5. 7F Swan-Ganz catheter with 0.035in. guide wire lumen (Arrow® or equivalent) or an angled pigtail catheter.
6. 3-way stopcock – with Luer-lock connectors.
7. Infusion pump and IV tubing for r-tPA infusion.
8. Heparinized saline for flushing.
9. 0.9% NaCl intravenous (IV) infusion bag 250cc for r-tPA pulse spray mixture.
10. IV infusion pump and tubing.
11. Sterile water for injection, USP (Do not use bacteriostatic water, USP for injection) - for 2mg vial Cathflo Alteplase (r-tPA) mixture (Genentech, Inc., South San Francisco, CA).
12. Pulse Spray r-tPA vials:
 - i. Unilateral PE:
 1. One (1) 2.2mg vial of Cathflo Alteplase (r-tPA) for pulse spray use.
 2. Two (2) 10cc syringes for injecting the pulse sprays.
 - ii. Bilateral PE:

1. Two (2) 2.2mg vials of Cathflo Alteplase (r-tPA) for pulse spray use.
2. Four (4) 10cc syringes for injecting the pulse sprays.

13. r-tPA Infusion:

- i. **Unilateral PE:** Obtain five (5) 2.2mg vials of Cathflo Alteplase (r-tPA) for continuous infusion to be started in the IR suite/Cath lab at the end of the procedure for a total of 10 mg for one infusion. *Mixture requirements are in section 9.3.*
- ii. **Bilateral PE:** Obtain five (5) 2.2mg vials of Cathflo Alteplase (r-tPA) for continuous infusion to be started in the IR suite/Cath lab at the end of the procedure for a total of 5 mg for each infusion for two infusions. *Mixture requirements are in section 9.3.*

